7.3 Blinding

This is a non-randomized, open-label study and blinding procedures are not applicable.

7.4 Dosage Modification

For Parts 1A, 1B, 2A, and 2B intra-participant dose escalation/reduction of BMS-986207, nivolumab, or ipilimumab is not permitted in this study in order to allow better evaluation of the safety and efficacy at individual dose levels and schedules except as described for the Preliminary

Safety Cohort (see [Section 5.1.2.3](#)). For intra-participant dose reduction of BMS-986207 in Part 1C and 2C, see [Section 5.1.2.6](#) and [Section 5.1.2.7](#), respectively.

7.4.1 Dose Limiting Toxicities

For the purpose of guiding dose escalation, DLTs will be defined based on the incidence, intensity, and duration of AEs for which no clear alternative cause is identified. The DLT period will be 28 days (4 weeks) in Parts 1A and 1B. The DLT period for Part 1C will be 42 days (6 weeks).

For the purpose of participant management, any AE that meets DLT criteria, regardless of the cycle in which it occurs, will lead to discontinuation of study drug unless the Investigator determines that only 1 of the agents must be discontinued due to toxicity attributed to that agent alone. Participants who withdraw from the study during the 4-week DLT evaluation period (6-week DLT evaluation period for Parts 1C and 2C) for reasons other than a DLT may be replaced with a new participant at the same dose level. The incidence of DLTs during the 4-week DLT evaluation period (6-week DLT evaluation period for Parts 1C and 2C) will be used in dose escalation decisions and to define the MTD. AEs occurring after the 4-week DLT period (6-week DLT evaluation period for Parts 1C and 2C) will be considered for the purposes of defining the RP2D upon agreement between the Sponsor, Medical Monitor, and Investigators.

Participants experiencing a DLT will not be retreated with study drug, and will enter the safety follow-up period of the study. DLTs occurring after the 4-week (or 6-week period for Parts 1C and 2C) DLT observation period will be accounted for in determining the RP2D for expansion.

AEs will be graded according to the NCI CTCAE v4.03.

7.4.1.1 Hepatic Dose-Limiting Toxicity

Any one of the following study drug-related events will be considered a hepatic DLT (except for HCC participants):

- Grade 4 elevations in serum transaminases (AST, ALT), alkaline phosphatase (ALP) or total bilirubin
- Grade 3 elevations in serum transaminases (AST, ALT) or alkaline phosphatase (ALP) that last longer than 5 days, or is associated with clinical symptoms, or bilirubin > 2 x ULN in the absence of cholestasis
- Grade 2 elevations in AST or ALT with symptomatic liver inflammation (eg, right upper quadrant tenderness, jaundice, pruritus)
- AST or ALT > 3 x ULN and concurrent total bilirubin > 2 x ULN without initial findings of cholestasis (elevated ALP, eg, findings consistent with Hy's law or FDA definition of potential drug-induced liver injury [pDILI]). Note that this specific category of DLT uses ULN rather than CTCAE grade for definition.

Hepatic DLT for HCC participants

- AST or ALT > 10 x ULN for > 2 weeks
- AST or ALT > 15 x ULN, irrespective of duration

- Total bilirubin $> 8 \times$ ULN, irrespective of duration for participants with elevated total bilirubin at study entry, or $> 5 \times$ ULN for those with normal total bilirubin at entry
- Concurrent ALT $\geq 10 \times$ ULN **AND** total bilirubin $\geq 2 \times$ ULN or baseline value (if elevated bilirubin at study entry), **AND** no other immediately apparent possible causes of ALT elevation and hyperbilirubinemia. (For definition of p-DILI, see [Section 9.2.7](#)).

7.4.1.2 Hematologic Dose-Limiting Toxicity

- Grade 4 neutropenia ≥ 7 days in duration
- Grade 4 thrombocytopenia
- Grade 3 thrombocytopenia with bleeding, or any requirement for platelet transfusion
- Febrile neutropenia
- Grade 3 hemolysis (ie, requiring transfusion or medical intervention such as steroids)
- Grade 4 anemia not explained by underlying disease

7.4.1.3 Dermatologic Dose-Limiting Toxicity

- Grade 4 rash
- Grade 3 rash if no improvement (ie, resolution to \leq Grade 1) after a 1 to 2 week infusion delay.

7.4.1.4 Other Dose-Limiting Toxicities

Any of the following events will be considered a DLT:

- Grade 2 drug-related uveitis, episcleritis, iritis eye pain or blurred vision that does not respond to topical therapy and does not improve to Grade 1 severity within the re-treatment period OR requires systemic treatment
- Grade 3 drug-related uveitis, episcleritis, iritis, pneumonitis, bronchospasm or neurologic toxicity
- Grade ≥ 4 hypersensitivity reaction or Grade 3 that does not resolve to Grade 1 in < 6 hours
- Other \geq Grade 3 study drug-related toxicity will be considered a DLT. However, the following Grade 3 or 4 events will **not** be considered DLTs:
 - Grade 3 or Grade 4 electrolyte abnormalities that are not complicated by associated clinical adverse experiences, last less than 48 hours and either resolve spontaneously or respond to conventional medical intervention
 - Grade 3 nausea, vomiting, or diarrhea that lasts less than 48 hours, and either resolves spontaneously or responds to conventional medical intervention
 - Grade 3 or grade 4 elevation of amylase or lipase not associated with clinical or radiographic evidence of pancreatitis
 - Grade 3 fever not associated with hemodynamic compromise (eg, hypotension, clinical or laboratory evidence of impaired end-organ perfusion)
- Grade 3 endocrinopathy that is well controlled by hormone replacement

- Grade 3 tumor flare (defined as pain, irritation, or rash that localizes to sites of known or suspected tumor)
- Grade 3 fatigue
- Grade 3 infusion reaction that returns to Grade 1 in < 6 hours

7.4.2 *Management Algorithms for Immuno-Oncology Agents*

Immuno-oncology agents are associated with immune-related AEs that can differ in severity and duration from AEs caused by other therapeutic classes. BMS-986207 and nivolumab are considered I-O agents in this protocol. Early recognition and management of immune-related AEs associated with I-O agents may mitigate severe toxicity. Management algorithms have been developed from extensive experience with nivolumab to assist Investigators in assessing and managing the following groups of immune-related AEs:

- Gastrointestinal
- Renal
- Pulmonary
- Hepatic
- Endocrinopathies
- Skin
- Neurological
- Myocarditis

The clinical nature of AEs events noted with BMS-986207 will determine the role of the algorithms for use in toxicities related to its use in this study. The algorithms recommended for the management of immune-related AEs in this protocol are in [Appendix 6](#).

7.4.3 *Dose Delays Due To Toxicity*

Participants who experience the following must have all study drug(s) withheld:

- Potential DLTs, until DLT relatedness is defined.
- Select AEs and laboratory abnormalities:
 - \geq Grade 1 pneumonitis
 - \geq Grade 2 abnormality in AST, ALT or total bilirubin
 - \geq Grade 2 creatinine
 - \geq Grade 2 diarrhea or colitis
 - \geq Grade 2 neurological AE
 - AE, laboratory abnormality, or concurrent illness that, in the judgment of the Investigator, warrants delaying study drug administration.
- Confirmed SARS-CoV-2 infection.

Criteria for participants who are required to permanently discontinue both study drugs is listed in [Section 8.2](#). Participants not meeting guidelines for permanent discontinuation will be permitted to resume therapy based on the criteria specified below in [Section 7.4.3.3](#). Participants eligible to resume study therapy will resume study therapy at the nominal treatment visit following their last received study medication dose.

The end of cycle tumor assessments, such as computed tomography (CT), magnetic resonance imaging (MRI), or positron emission tomography (PET), will continue on a q8w schedule relative to the participant's first dose, regardless of any treatment delay incurred.

7.4.3.1 *Criteria for Dose Delay Secondary to Changes in AST or ALT for Participants with HCC*

Participants with HCC who experience the following must have the study drug delayed:

- 1) If a participant has a baseline AST or ALT that is within normal limits, delay dosing for drug-related \geq Grade 2 toxicity (2 grade shift)
- 2) If a participant has baseline AST or ALT within the Grade 1 toxicity range, delay dosing for drug-related \geq Grade 3 toxicity (2 grade shift)
- 3) If a participant has baseline AST or ALT within the Grade 2 toxicity range, delay dosing for a 2-fold drug-related increase in AST or ALT or for AST or ALT values $8 \times$ ULN (whichever is lower)
- 4) Hepatic DLT as defined in [Section 7.4.1.1](#)

It is recommended to monitor elevations in AST or ALT approximately every 3 days until levels peak and begin to decline. BMS-986207 dosing can be resumed where criteria to resume treatment are met ([Section 7.4.3.3](#))

7.4.3.2 *Protocol-Specific Recommendation for Management of Hepatic Events in HCC Participants*

The algorithms recommended for the management of immune-related AEs in this protocol are in [Appendix 6](#). Protocol-specific recommendation for the management of hepatic events in HCC participants are as follows:

- Dose delay criteria for hepatic events are outlined in [Section 7.4.3.1](#). If AST or ALT levels do not improve with a dose delay of 3 to 5 days, or if the levels worsen, steroid therapy should be initiated at 0.5 to 2 mg/kg/day methylprednisolone or oral equivalent
- For ALT or AST levels $> 8 \times$ ULN, steroid therapy should be initiated promptly at 1 to 2 mg/kg/day methylprednisolone IV, intramuscularly, or oral equivalent
- For all participants receiving steroid treatment for hepatic events, the BMS Medical Monitor should be consulted within 24 hours after initiation of steroids. Gastroenterology consult is recommended
- If AST or ALT levels do not improve within 3 to 5 days after the start of steroid therapy, or the levels worsen after the start of steroid therapy, discussion with the BMS Medical Monitor regarding the possibility of adding mycophenolate mofetil 1 g twice daily should occur

- Tapering of steroids can start once AST or ALT levels have declined by 1 CTCAE grade. Steroids should be tapered slowly, over no less than 1 month

As outlined in Section 7.4.3.3, study therapy may resume when AST or ALT have returned to Grade 1 or baseline unless the AE meets the criteria for permanent discontinuation ([Section 7.4.4](#)). The BMS Medical Monitor must be consulted prior to resuming nivolumab for all participants who required steroid intervention.

7.4.3.3 Criteria to Resume Treatment

Subsequent dosing with study therapy may resume once drug-related nonDLT AEs resolve to Grade 1 or baseline.

Participants experiencing AEs not meeting criteria for permanent discontinuation as outlined in [Section 7.4.4](#) may resume treatment with study medication under the following criteria:

- Participants may resume treatment with study drug when the drug-related AE(s) resolve to Grade \leq 1 or baseline value, with the following exceptions:
 - Participants may resume treatment in the presence of Grade 2 fatigue
 - Participants who have not experienced a Grade 3 drug-related skin AE may resume treatment in the presence of Grade 2 skin toxicity
 - Participants with Grade 2 uveitis, episcleritis, iritis, eye pain or blurred vision not meeting DLT criteria ([Section 8.2](#)) must resolve to baseline prior to resuming study therapy
- For participants with Grade 2 AST, ALT, or total bilirubin elevations, dosing may resume when laboratory values return to baseline, and management with corticosteroids (if needed), is complete
- Participants with combined Grade 2 AST/ALT **and** total bilirubin values meeting DLT criteria ([Section 7.4.1.1](#)) should have treatment permanently discontinued
- Participants with confirmed SARS-CoV-2 infection may resume treatment after 1) at least 10 days (20 days for severe/critical illness) have passed since symptoms first appeared, positive RT-PCR test result, or positive viral antigen test result; 2) resolution of acute symptoms (including at least 24 hours has passed since last fever without fever reducing medications); 3) evaluation by the Investigator with confirmation that there are no sequelae that would place the participant at a higher risk of receiving investigational treatment; and 4) consultation by the Medical Monitor. For suspected cases, treatment may also resume if SARS-CoV-2 infection is ruled-out and other criteria to resume treatment are met.
- Prior to re-initiating on-study treatment in a participant with a dosing delay lasting 8 weeks due to SARS-CoV-2 infection, the Medical Monitor/designee must be consulted.
- **Criteria for HCC Participants:**
 - Participants with baseline Grade 1 AST, ALT, or total bilirubin who require dose delays, for reasons other than a drug-related hepatic event, may resume treatment in the presence of Grade 2 AST, ALT, or total bilirubin increases.

- Participants who require dose delays for drug-related increased AST, ALT, or bilirubin may resume treatment when hepatic parameters are at baseline or Grade 1, and after discussion with the BMS Medical Monitor
- Participants with AST, ALT or bilirubin values meeting permanent discontinuation parameters (Section 7.4.4) should have treatment permanently discontinued
- Drug-related pulmonary toxicity, diarrhea, or colitis, must have resolved to baseline before treatment is resumed. Participants with persistent Grade 1 pneumonitis after completion of a steroid taper over at least 1 month, may be eligible for retreatment if discussed with, and approved by, the BMS Medical Monitor
- Participants with drug-related endocrinopathies adequately controlled with only physiologic hormone replacement, may resume treatment

If the criteria to resume treatment are met, the participant should restart treatment at the next nominally scheduled timepoint per protocol.

Even if the criteria to resume treatment are met, the consideration to re-initiate study therapy under the following exception will be made on a case by case basis after considering the overall benefit/risk profile, and in consultation between the Investigator and the Sponsor. Any AE with clinical risk will be assessed on a case by case basis with the Investigator and the BMS Medical Monitor, to determine the risks and benefits of continuing on therapy following resolution versus discontinuing therapy permanently.

7.4.4 *Exceptions to Permanent Discontinuation Criteria*

Any drug-related AE occurring at any time that meets DLT criteria as outlined in [Section 7.4.1](#) will require permanent discontinuation unless the Investigator determines that only 1 of the agents must be discontinued due to toxicity attributed to that agent alone, **with the exception of the following:**

- Grade 3 diarrhea, nausea, vomiting, or abdominal pain that returns to Grade 1 or baseline within 3 days with medical intervention
- Grade 3 pruritus or rash that returns to Grade 1 or baseline within 7 days with medical intervention
- Isolated Grade 3 or 4 electrolyte imbalances/abnormalities that are not associated with clinical sequelae and are corrected with supplementation/appropriate management within 3 days of their onset
- Grade 4 neutropenia < 7 days in duration
- Grade 4 lymphopenia or leukopenia
- Grade 3 or 4 increase in amylase or lipase that is not associated with clinical or radiographic evidence of pancreatitis
- Grade 3 infusion reactions that return to Grade 1 in < 6 hours
- Grade 3 fever not associated with hemodynamic compromise (eg, hypotension, clinical, or laboratory evidence of impaired end-organ perfusion)

- Grade 3 tumor flare (defined as pain, irritation, or rash that localizes to sites of known or suspected tumor)
- Grade 3 fatigue
- Grade 3 or 4 drug-related endocrinopathy AEs, such as adrenal insufficiency, adrenocorticotropic hormone, hyper- or hypothyroidism, or glucose intolerance, which resolve or are adequately controlled with physiologic hormone replacement (corticosteroids, thyroid hormones) or glucose-controlling agents, respectively, may not require discontinuation after discussion with and approval from the BMS Medical Monitor
- Any event that leads to delay in dosing, lasting > 6 weeks from the previous dose, requires discontinuation, with the exception of the following:
 - Dosing delays to allow for prolonged steroid tapers to manage drug-related AEs are allowed. Prior to re-initiating treatment in a participant with a dosing delay lasting > 6 weeks from the previous dose, the BMS Medical Monitor must be consulted. Tumor assessments should continue as per protocol even if dosing is delayed. Periodic study visits to assess safety and laboratory studies should also continue every 6 weeks, or more frequently if clinically indicated, during such dosing delays.
 - Dosing delays lasting > 6 weeks from the previous dose that occur for non drug-related reasons may not require discontinuation, if approved by the BMS Medical Monitor. Prior to re-initiating treatment in a participant with a dosing delay lasting > 6 weeks, the BMS Medical Monitor must be consulted.
- Any AE, laboratory abnormality, or intercurrent illness which, in the judgment of the Investigator, presents a substantial clinical risk to the participant with continued nivolumab dosing.

All participants who discontinue IP should comply with protocol specified follow-up procedures as outlined in [Section 8.2](#). The only exception to this requirement is when a participant withdraws consent for all study procedures including post treatment study follow-up or loses the ability to consent freely (eg, imprisonment, involuntarily incarceration for the treatment of either a psychiatric or physical illness).

If study treatment is discontinued prior to the participant's completion of the study, the reason for the discontinuation must be documented in the participant's medical records and entered on the appropriate case report form (CRF) page.

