5.1.2.5 Dose Limiting Toxicities in Dose Escalation Phases (Parts 1A and 1B)

For the purpose of guiding dose escalation, DLTs will be defined based on the incidence, intensity, and duration of AEs for which no clear alternative cause is identified. The DLT period will be 28 days (4 weeks) in Part 1A and 28 days (4 weeks) in Part 1B. Any toxicities that occur beyond the 4-week DLT period will be accounted for in making dose level decisions.

For the purpose of participant management, any AE that meets DLT criteria, regardless of the cycle in which it occurs, will lead to discontinuation of study drug. Participants who withdraw from the study during the DLT evaluation period for reasons other than a DLT may be replaced with a new participant at the same dose level. The incidence of DLT(s) during the DLT evaluation period will be used in dose escalation decisions and to define the MTD. AEs occurring after the 4-week DLT evaluation period will be considered for the purposes of defining the RP2D upon agreement between the Sponsor, Medical Monitor, and Investigators, if the AEs are determined to have no clear alternative cause and are not related to disease progression.

Participants experiencing a DLT will not be retreated with study drug and will enter the safety follow-up period of the study. AEs will be graded according to the NCI CTCAE v4.03.

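### Sections 7.4.1, 5.1.2.5 and the Synopsis stop study drug after a DLT, Sections 7.4.4 and 8.1 let some of the same DLTs continue, and the exception list itself holds two stopping criteria

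*Combined protocol and SAP*

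**What the plan says.** **Sections that stop treatment.** Section 7.4.1 says that an AE meeting DLT criteria "will lead to discontinuation of study drug unless the Investigator determines that only 1 of the agents must be discontinued due to toxicity attributed", which limits the exception to toxicity from a single drug. It then adds, without qualification: "Participants experiencing a DLT will not be retreated with study drug, and will enter the safety follow-up period of the study". The Synopsis has the same two statements. Section 5.1.2.5, which covers Parts 1A and 1B, says that "any AE that meets DLT criteria, regardless of the cycle in which it occurs, will lead to discontinuation of study drug" and gives no exception, not even for a single agent. None of these three places mentions Section 7.4.4.

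**Sections that allow continuation.** Section 7.4.4 restates the Section 7.4.1 rule with the single-agent provision, then lists exceptions to it. The first is "Grade 3 diarrhea, nausea, vomiting, or abdominal pain that returns to Grade 1 or baseline within 3 days with medical intervention". Section 8.1, the list of mandatory reasons to stop, refers to Section 7.4.4 for these exceptions.

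**A section that faces both ways.** Section 7.4.3.3 opens by allowing dosing to resume after drug-related AEs that are not DLTs. Its next sentence makes resumption depend on Section 7.4.4.

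**Stopping criteria among the exceptions.** Under the same lead-in, Section 7.4.4 places a dosing delay of more than 6 weeks, which it says requires discontinuation. It also places any AE, laboratory abnormality or illness that in the investigator's judgment "presents a substantial clinical risk to the participant with continued nivolumab dosing".

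**Pointers.** Section 7.4.3 states "Criteria for participants who are required to permanently discontinue both study drugs is listed in" Section 8.2. Section 7.4.3.3 also cites Section 8.2, for the DLT criteria for eye events.

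**The concern.** A site managing a participant with a DLT needs one answer on whether study drug stops. Here the answer depends on which section is opened. Three things ride on it: whether the participant receives more drug after a toxicity that the protocol calls dose-limiting, the exposure recorded at that dose level, and the count of AEs leading to discontinuation. That count is among the primary endpoints for every part of the study in Table 4-1. If sites apply different rules, part of the difference in discontinuations between dose levels or cohorts could reflect which section was followed, not how well the dose was tolerated.

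**Working it through.** The plan states no figure on this point, so the check is a comparison of definitions. Section 7.4.4 has 13 bullets at the first level: 11 name event types and 2 are the stopping criteria described above. Each event type was compared with the DLT definitions in Sections 7.4.1.1 to 7.4.1.4. The general clause in Section 7.4.1.4 makes other drug-related toxicity of Grade 3 or higher a DLT unless it is on the list of exclusions.

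| Section 7.4.4 exception | Kept off the DLT list by Section 7.4.1.4 | Both a DLT and excepted |
|---|---|---|
| Grade 3 nausea, vomiting or diarrhoea, resolved within 3 days | Only if under 48 hours | 48 hours up to 3 days |
| Grade 3 abdominal pain, resolved within 3 days (same bullet) | Not excluded | Any such event |
| Isolated Grade 3 or 4 electrolyte abnormality, corrected within 3 days | Only if under 48 hours and uncomplicated | 48 hours up to 3 days |
| Grade 3 or 4 endocrinopathy, controlled, with Medical Monitor approval | Grade 3 only | Grade 4 |
| Grade 4 lymphopenia or leukopenia | Not excluded, but also absent from the haematologic list in Section 7.4.1.2 | Only if the general clause reaches haematologic events |
| Grade 3 pruritus, resolved within 7 days | Not excluded, but also absent from the dermatologic list in Section 7.4.1.3 | Only if the general clause reaches skin events |

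The gastrointestinal exclusion is "Grade 3 nausea, vomiting, or diarrhea that lasts less than 48 hours", with spontaneous resolution or response to conventional treatment. Three days is 3 × 24 = 72 hours, so the overlap window is 72 − 48 = 24 hours wide.

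Take a drug-related Grade 3 diarrhoea that returns to Grade 1 at 60 hours with treatment, in Part 1A or 1B:

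- 60 ≥ 48, so it is a DLT under Section 7.4.1.4.
- Sections 5.1.2.5 and 7.4.1 then end treatment.
- 60 ≤ 72, so Sections 7.4.4 and 8.1 do not require treatment to end.

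The other six event types create no conflict because they are not DLTs: neutropenia under 7 days, amylase or lipase elevation without pancreatitis, infusion reaction resolving in under 6 hours, fever without haemodynamic compromise, tumour flare, and fatigue. Grade 3 rash resolving within 7 days is also not a DLT under Section 7.4.1.3.

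The count of event-type bullets is therefore 3 clear overlaps (gastrointestinal, electrolyte, endocrine), 2 that depend on the general clause, and 6 with none: 3 + 2 + 6 = 11.

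**The two stopping criteria.** The delay bullet says itself that discontinuation is required, so its meaning survives its position. The substantial-risk bullet has no verb of its own and takes its meaning from the lead-in. Read literally, it exempts such an event from stopping. Section 8.1 requires stopping for a closely similar criterion, an AE that in the investigator's opinion makes continued participation contrary to the participant's interest.

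**The pointers.** Section 8.2 deals with withdrawal from the study and withdrawal of consent. It has neither permanent-discontinuation criteria nor eye DLT criteria. The eye criteria are in Section 7.4.1.4.

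**The case against.** The best defence is that this is a general rule with stated exceptions. Section 7.4.4 is titled as exceptions and cites Section 7.4.1 by number, and Section 8.1 repeats the rule and sends the reader to the list. A site that starts from Section 8.1 reaches one answer. This softens the conflict but does not remove it. Sections 7.4.1 and 5.1.2.5 and the Synopsis do not send the reader to the list, and the no-retreatment sentence is unqualified. That sentence does not even repeat the single-agent provision that precedes it. Nor can it be taken to mean only retreatment at a later progression, because it also moves the participant into safety follow-up.

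It is also fair that a site is unlikely to read a substantial-risk bullet as permission to continue, especially with Section 8.1 in hand. That limits the practical risk. The wording still says the opposite of what appears to be meant.

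A reader might infer more than the documents support:

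- **That HCC sites have no hepatic stopping limits.** Section 7.4.3.3 refers to "Participants with AST, ALT or bilirubin values meeting permanent discontinuation parameters" and cites Section 7.4.4, which lists no values. But Section 7.4.4 opens by requiring discontinuation for events that meet DLT criteria under Section 7.4.1, and Section 7.4.1.1 gives numeric limits for HCC participants. The limits exist, one step further on.
- **That the discontinuation rate would shift by a known amount.** One event in 6 participants is 1/6 = 16.7 percentage points, and one in 18, the Part 1C maximum per dose level, is 1/18 = 5.6. The documents give no frequency for the overlapping events, so neither figure estimates an effect.
- **That dose decisions are distorted.** The BLRM and BOIN rules count DLTs by the Section 7.4.1 definitions, which do not depend on whether treatment continues.

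**Conclusion.** The contradiction stands. It covers Grade 3 nausea, vomiting or diarrhoea and Grade 3 or 4 electrolyte abnormalities lasting from 48 hours up to 3 days, Grade 3 abdominal pain resolving within 3 days, and controlled Grade 4 endocrinopathy where the Medical Monitor approves continuation. It extends to Grade 4 lymphopenia or leukopenia and Grade 3 pruritus only if the general clause in Section 7.4.1.4 is meant to cover haematologic and skin events outside their own lists, which the protocol does not settle. In addition, two stopping criteria are misplaced and two pointers to Section 8.2 are wrong.

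The exception-free rule in Section 5.1.2.5 applies to Parts 1A and 1B. For the other parts the conflict is between Section 7.4.1 with the Synopsis and Section 7.4.4 with Section 8.1. The consequences are for participant management, exposure and the primary endpoint of AEs leading to discontinuation, which Section 10.3.2 summarises descriptively. No test, sample size or DLT count changes. This is an inconsistency in an operative stopping rule and should be corrected. The documents do not show which rule is intended for each overlapping event, and this review takes no position on that.

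**What to change.** 1. Reconcile Sections 5.1.2.5, 7.4.1, 7.4.3.3, 7.4.4 and 8.1 and the Synopsis into one rule, stated once and cited elsewhere. The sponsor decides which rule stands for each overlapping event, and whether the general clause in Section 7.4.1.4 reaches lymphopenia, leukopenia and pruritus.
2. State whether the single-agent provision qualifies the no-retreatment sentence, and whether it applies under Section 5.1.2.5.
3. Move the delay and substantial-risk bullets out of the Section 7.4.4 exception list and give them their own lead-in as stopping criteria.
4. Correct the two Section 8.2 pointers in Sections 7.4.3 and 7.4.3.3.
5. As a minor clarification, have the HCC text in Section 7.4.3.3 cite Section 7.4.1.1 directly.

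The cost is wording in the next amendment, with no added participants or assessments.
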